**CHARACTERIZATION OF CHANGES IN PERITONEAL CELLS GENE
EXPRESSION AFTER STANDARD VERSUS LOW PRESSURE LAPAROSCOPIC
CHOLECYSTECTOMY AND ITS CLINICAL CORRELATION.**

PROTOCOL

NCT03020641

January 27, 2017

INSTITUTION NAME: Ramón y Cajal Hospital. Madrid, Spain.

PRINCIPAL INVESTIGATORS: [name] and [name].

TITLE OF THE RESEARCH PROJECT: Characterization of changes in peritoneal cells gene expression after standard versus low pressure laparoscopic cholecystectomy and its clinical correlation.

HYPOTHESES

We hypothesized that applying a low intraperitoneal pressure of pneumoperitoneum ($\leq 8\text{mmHg}$) during laparoscopic cholecystectomy, the adverse impact on the surgical peritoneal environment (measured as gene expression of extracellular matrix adhesion and inflammatory cytokine and apoptotic index), can be minimized and probably clinical outcomes might be better.

OBJECTIVES

Primary Objective.

To characterize the changes produced in gene expression (mRNA) levels of remodelling and inflammatory markers as well as to measure apoptotic index, in peritoneal tissue, after laparoscopic cholecystectomy with low and standard pneumoperitoneum pressures ($\leq 8\text{mmHg}$ vs $\geq 12\text{mmHg}$).

The primary aim of this study is to analyse differences in those variables between both intraperitoneal pressure groups at different times: Before starting surgery (T0) and 60 minutes after surgery started.

Secondary Objectives.

To analyse within groups (high and low pressure) differences between times T0 and T1 in the same remodelling and inflammatory physiological parameters. To analyse the effect of intraperitoneal pressure in outcomes (see below).

STUDY DESIGN

This is a prospective randomized and blinded controlled trial to assess the potential adverse impact of pneumoperitoneum during laparoscopic cholecystectomy on peritoneal tissue at two different working pressures and at two different times and to correlate it with clinical outcomes as well.

STUDY GROUPS

- A. **Intervention group:** in all patients allocated to the intervention group laparoscopic cholecystectomy will be performed with pneumoperitoneum pressure (PnPr) at or below 8 mm Hg. To ease this goal deep neuromuscular block will be provided with

rocuronium till the end of surgery. Neuromuscular block will be reversed with sugammadex at a dose of 4mg/kg.

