B. **Control group:** In patients allocated to this group laparoscopic cholecystectomy with abdominal pressure at 12 mm Hg or higher will be performed. In this group the level of neuromuscular block and its reversion will be done in the same way as in the intervention group.

POPULATION

Reference population: Patients undergoing elective laparoscopic cholecystectomy.

Eligibility: Patients older than 18 years, signed informed consent, undergoing laparoscopic cholecystectomy for symptomatic cholelithiasis or gallbladder polyps.

Exclusion criteria:

- Emergency surgery.
- Previous surgery at supramesocolic compartment.
- Previous peritoneal inflammatory process.
- Pregnancy or breastfeeding.
- Patient refusal to participate in the study.

RANDOMIZATION

Patients will be randomly assigned to the control or intervention group according to a simple randomization list generated by Query v.7. Allocation will be concealed till the surgical intervention date using sealed opaque numbered envelopes.

MAIN VARIABLES IN THIS STUDY ARE:

- Inflammatory peritoneal markers: (gene expression (mRNA) levels of):

- IL-1, IL-6, IL-10.
- VEGF-A “vascular endothelial growth factor A”.
- TNF α “tumor necrosis factor α ”.
- CXCL-2 “chemokine CXC ligand 2”.

- Remodeling peritoneal markers: (gene expression (mRNA) levels of):

- CTGF “connective tissue growth factor”.
- MMP-9 “matrix metalloproteinase-9”.
- PAI-1 “plasminogen activator inhibitor-1”.
- E-selectine.

- Apoptotic index.

SECONDARY VARIABLES ARE:

During the intraoperative period:

- Surgical Rating Score (SRS) to measure the working space during this laparoscopic surgery (optimal, good, acceptable, poor or very poor conditions).
- The need to change initial intraperitoneal PnPr (yes/no).
- Subjective sensation of the PnPr performed (standard or low) reported by the main surgeon (consistent vs inconsistent).
- Peak inspiratory pressure and tidal volume (mmHg).
- Total Co₂ volume administered during pneumoperitoneum (L).
- Total dose of sugammadex (mg).

During postoperative period:

- Pain measured by visual analogue scale (VAS) from 0 to 10.
- Time to start oral intake (in hours).
- Time to start ambulation (in hours).
- Long of hospital stay (in days).

STATISTICAL ANALYSIS

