Biomarker data will be log-transformed before data analysis to make these variables to follow a normal distribution. Continuous variables will be expressed as mean and standard deviation. Categorical variables will be expressed as numbers and proportions. Between groups comparisons at T0 and T1 will be made by means of t-Student test. In case of non-normal distribution despite log-transformation of data we used a non-parametric alternative (U-Mann-Whitney test) instead. We will also compare within groups means differences between times T1 and T0. For this comparison we will use paired t-student test or McNemar test for normal or non-normal variable distributions respectively. Covariance analysis will be used to compare the effect of high and low pressure on parameter analysed adjusting for baseline value of the biomarker. Normality tests will be based on Kolmogorov- Smirnov. All analysis will be performed using STATA 13 (STATAcorp.2013. Stata Statistical Software: Release13. College Station, TX: StataCorpLP).

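### The primary aim compares the pressure groups before surgery, and at T1 the plan does not say whether the unadjusted test or the baseline-adjusted ANCOVA decides the result

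*Combined protocol and SAP*

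**What the plan says.** The protocol's Primary Objective opens with a statement about change: "To characterize the changes produced in gene expression (mRNA) levels of remodelling and inflammatory markers as well as to measure apoptotic index". The primary aim that follows is worded differently. It is to "analyse differences in those variables between both intraperitoneal pressure groups at different times: Before starting surgery (T0) and 60 minutes after surgery started".

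The Statistical Analysis section gives three instructions that bear on this aim:

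- An unadjusted test at each time: "Between groups comparisons at T0 and T1 will be made by means of t-Student test".
- A fallback for that test: "In case of non-normal distribution despite log-transformation of data we used a non-parametric alternative (U-Mann-Whitney test) instead". Normality is judged by Kolmogorov-Smirnov.
- A baseline-adjusted analysis: "Covariance analysis will be used to compare the effect of high and low pressure on parameter analysed adjusting for baseline value of the biomarker".

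No sentence calls any of these primary, secondary or sensitivity, and none says what happens if they disagree. T1 is never formally defined. I take it as the 60-minute point, since the design has only two times. Within-group T0–T1 comparisons are a secondary objective.

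**The concern.** There are two problems.

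**The T0 comparison.** T0 comes before the randomised pressure is applied. If randomisation and sampling are sound, any T0 difference between arms is chance, and a T0 test says nothing about pressure. Allocation is by simple randomisation, so nothing in the design limits such imbalances. The unadjusted T1 test does not correct for them either. When T0 and T1 are correlated, a chance imbalance carries into the T1 t-test in its own direction and can create an apparent pressure effect or hide a real one.

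**Two answers at T1.** The t-test (or Mann-Whitney) and the ANCOVA both address the effect of pressure on the same marker. The wording of the primary aim matches the t-test sentence, but only the ANCOVA sentence speaks of a pressure effect. A reader cannot tell which one decides, so the result that is stressed could be chosen after both are seen. The ANCOVA sentence also has no stated alternative for non-normality, so its standing is unclear for a marker that has moved to Mann-Whitney.

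**Working it through.** The plan states no figure on this point, so there is nothing to reproduce.

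**Inputs from the documents.** Two arms; simple randomisation; log-transformed markers; 11 main variables (6 inflammatory + 4 remodelling + apoptotic index).

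**Assumed, because the documents are silent.** 30 per arm, two-sided 0.05, T0–T1 correlation r = 0, 0.3, 0.5 or 0.7, bivariate normal values on the log scale, equal variances, equal arms.

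**Step 1: T0 tests.** With 11 tests at 0.05, the expected number of significant T0 differences is 11 × 0.05 = 0.55. If markers were independent, the chance of at least one is 1 − 0.95^11 = 43.1%. None would be evidence about pressure.

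**Step 2: carry-over to T1.** With no true effect and a T0 statistic z0, the unadjusted T1 statistic is approximately normal with mean r·z0 and variance 1 − r². At z0 = 1.96 and r = 0.5 the mean is 0.98 and the SD 0.866. The chance of exceeding 1.96 is 1 − Φ((1.96 − 0.98)/0.866) = 1 − Φ(1.13), about 12.9%; the opposite tail is negligible. For r = 0.3 and 0.7 the result is 7.9% and 20.5%. These are for an imbalance just at the 5% threshold; the table averages over all significant imbalances.

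**Step 3: choosing between the T1 analyses.** In large samples the two T1 statistics have correlation √(1 − r²) = 0.954, 0.866, 0.714 for r = 0.3, 0.5, 0.7. The chance that at least one is significant under no effect is 1 − P(both within ±1.96) = 6.4%, 7.3%, 8.3%. Simulation at 30 per arm agrees. At r = 0 it gives 5.5%, because the fitted baseline slope is not exactly zero in a finite sample.

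**Step 4: power.** ANCOVA multiplies the variance of the effect estimate by about 1 − r² = 0.91, 0.75, 0.51. Standardised effects that give ANCOVA 80% power are d = 0.736, 0.702, 0.637, 0.525 for r = 0, 0.3, 0.5, 0.7. The T1 t-test then has non-centrality d·√(30/2) = 2.85, 2.72, 2.47, 2.03, and hence the powers in the table.

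| 30 per arm, per marker | r = 0 | r = 0.3 | r = 0.5 | r = 0.7 |
|---|---|---|---|---|
| No effect: either T1 analysis significant | 5.5% | 6.4% | 7.3% | 8.3% |
| No effect, T0 significant: T1 t-test rejects | 5.0% | 9.4% | 18.0% | 32.6% |
| Effect: T1 t-test power (ANCOVA 80%) | 80.0% | 76.2% | 68.0% | 51.7% |
| Effect: the two disagree on significance | 2.6% | 7.7% | 16.6% | 32.6% |
| Effect, T0 significantly against it: t-test power | 79.6% | 52.4% | 24.2% | 2.9% |
| Effect, T0 significantly with it: t-test power | 79.2% | 92.7% | 96.4% | 98.7% |

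The power row is analytic; the other rows are simulated (1,000,000 trials per null cell, 200,000 per effect cell). With no effect and a significant T0, ANCOVA rejects in 4.8–5.2%. With an effect and a significant T0 in either direction, its power is 75.0–76.8%.

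**Step 5: sensitivity.** From 20 to 50 per arm, the first row moves by at most 0.3 points and the second by less than 1 point. Repeating the null cells with simple randomisation instead of equal arms did not change them materially. With exponential, heavy-tailed (t, 3 df) or lognormal baselines and errors, ANCOVA rejected a true null in 3.9–4.9% of trials, so non-normality alone did not inflate its error in these cases.

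**The case against.** The best defence is that the plan already contains the right analysis. The ANCOVA is prespecified without conditions, is the only analysis tied to a pressure effect, and suits the opening objective about changes. On that reading the t-tests are by-time descriptions and only a label is missing. The reading is possible, but the plan does not state it, and the primary aim's own wording points to the other test.

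The aim speaks of analysing differences at T0, not testing them. That is true of the Objectives section alone; the test comes from the Statistical Analysis section. A T0 p-value biases no T1 estimate, and no later step depends on it. The objection therefore limits the harm of the T0 test itself, but not the case for taking T0 out of the primary aim.

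The starkest figures are conditional. A significant T0 occurs in about 5% of trials per marker, and one running against the effect in about 2.5%. Unconditionally the T1 t-test is valid, and the inflation from choosing arises only if the choice is in fact made on significance. This stands. The power loss and the disagreement rate are the stronger evidence, and they too depend on an unknown r.

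Multiplicity over 11 markers is larger: 43.1% for at least one false positive with a single T1 test each, if independent, against 51.7–61.3% when either analysis may be chosen (r = 0.3 to 0.7). Ranking the analyses does not settle that separate matter.

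**Conclusion.** The concern holds. As written, part of the primary aim concerns a difference that pressure cannot have caused, and each of the 11 main variables has two unranked T1 analyses. The unconditional cost of free choice is modest, 5.5–8.3% instead of 5% per marker. The loss from relying on the unadjusted test is negligible at r = 0 and large at r = 0.7. At r = 0.5 the two analyses would disagree in about one trial in six under the assumed effect. All sizes rest on the assumed 30 per arm, two-sided 0.05 and range of r. The gap in the specification does not depend on those assumptions. More than a label is at stake, since the test that the primary aim points to would give way to a more precise one that corrects for chance baseline imbalance.

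**What to change.** - Name the planned ANCOVA of log T1 on arm and log T0 as the single primary between-group analysis for every marker. Report the adjusted effect with a 95% CI, as a geometric-mean ratio where the log scale applies. Define the scale of the apoptotic index first.
- Do not switch this analysis on the Kolmogorov-Smirnov result. Give a rank-based or robust baseline-adjusted analysis, and the unadjusted T1 t-test or Mann-Whitney, as sensitivity analyses.
- Report T0 by arm descriptively, without a test.
- Restate the primary aim as the between-group difference at T1 adjusted for T0, and define T1.
- Keep the within-group comparisons as a secondary objective, not as evidence of a pressure effect.

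The essential part is the ranking and the removal of the T0 test. The cost is a few sentences in the objectives and analysis sections and no new data. ANCOVA spends one degree of freedom: at 30 per arm and r = 0, simulated power is 79.3% against 79.9% for the t-test. It also needs a rule for patients without a usable T0 value. For a marker that stays heavily skewed or heavy-tailed after logging, a rank-based test may have more power, and keeping it as a sensitivity analysis accepts that loss.

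### The fallback for non-normal within-group T0–T1 comparisons is McNemar's test, which does not apply to expression levels; a paired rank test should be named instead

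*Combined protocol and SAP*

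**What the plan says.** The first secondary objective is a paired comparison in each arm: "To analyse within groups (high and low pressure) differences between times T0 and T1 in the same remodelling and inflammatory physiological parameters". The main variables are quantitative. Two lists open with "Inflammatory peritoneal markers: (gene expression (mRNA) levels of" and "Remodeling peritoneal markers: (gene expression (mRNA) levels of", and the apoptotic index follows.

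The Statistical Analysis section log-transforms the biomarkers and describes this comparison as one of means: "We will also compare within groups means differences between times T1 and T0". It then names the tests: "For this comparison we will use paired t-student test or McNemar test for normal or non-normal variable distributions respectively". Normality is to be judged as follows: "Normality tests will be based on Kolmogorov- Smirnov".

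For the between-group comparison, the same section provides a rank test as the fallback: "In case of non-normal distribution despite log-transformation of data we used a non-parametric alternative (U-Mann-Whitney test) instead".

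**The concern.** McNemar's test takes a two-by-two table of a binary variable observed twice on the same patients and uses only the discordant pairs. It is not a distribution-free counterpart of the paired t-test for quantitative data. Two expression levels per patient give no such table until someone sets a cut-off, and the plan sets none.

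If a marker fails the normality check after log-transformation, the analyst must either invent a cut-off, read McNemar as a sign test on the direction of change, or substitute another test. None of these is pre-specified. Unless the text is corrected first, the choice would be made with the data in hand, and the options can give different answers.

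**Working it through.** **1. Does any variable in the plan suit McNemar?**

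- *Main variables.* Six inflammatory markers (IL-1, IL-6, IL-10, VEGF-A, TNFα, CXCL-2) and four remodelling markers (CTGF, MMP-9, PAI-1, E-selectin), all expression levels, plus the apoptotic index. There is no threshold or responder definition anywhere.
- *Secondary variables.* Two are binary: "The need to change initial intraperitoneal PnPr (yes/no") and whether the surgeon's impression of the pressure was consistent. Both are listed as intraoperative variables, and neither is described as measured at T0 and again at T1.

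The sentence also ties McNemar to non-normality, not to binary data. It therefore cannot be read as a provision for categorical variables.

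**2. How many tests are exposed?** (6 + 4) markers × 2 arms = 20; with the apoptotic index, 11 × 2 = 22. This is a ceiling, because only markers that fail the normality check reach the branch.

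**3. Does the missing cut-off matter?** With b and c discordant pairs in the two directions, the exact two-sided p-value is 2 × P(X ≤ min(b, c)), where X ~ Binomial(b + c, ½). One simulated set of 30 pairs (normal data, used only to show dependence on the cut-off) gave:

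| Cut-off (T0 percentile) | Discordant pairs | Exact McNemar p |
|---|---|---|
| 25th | 0 vs 5 | 2 × 1/32 = 0.06 |
| 50th | 3 vs 7 | 2 × 176/1024 = 0.34 |
| 75th | 4 vs 10 | 2 × 1471/16384 = 0.18 |
| 90th | 1 vs 6 | 2 × 8/128 = 0.13 |

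The Wilcoxon signed-rank test on the same pairs gave p = 0.002.

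**4. Illustrative power.** The documents give no sample size, effect size or correlation, so every input here is an assumption: 30 pairs, T0–T1 correlation 0.5, two-sided 5% level, 5,000 replicates. With unit SD at each time, the SD of the difference is √(2 × (1 − 0.5)) = 1. The shift is set to give the paired t-test 80% power under normality. Solving P(T > 2.045) = 0.80 for a non-central t with 29 degrees of freedom and non-centrality shift × √30 gives a shift of about 0.53 SD. Non-normal data are then drawn with that shift:

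| Test | Skewed (exponential components) | Heavy-tailed (t, 3 df) |
|---|---|---|
| Wilcoxon signed-rank | 0.87 | 0.92 |
| McNemar as a sign test | 0.85 | 0.85 |
| McNemar, pooled-median cut | 0.45 | 0.63 |
| McNemar, T0-median cut | 0.57 | 0.59 |
| McNemar, pooled 75th-percentile cut | 0.19 | 0.44 |

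The McNemar rows use the exact test. The loss against Wilcoxon runs from 0.87 − 0.85 = 2 points to 0.87 − 0.19 = 68 points. The four McNemar readings disagree on significance in 77% (skewed) and 65% (heavy-tailed) of data sets. With no true change, taking the most favourable of the four gives 7.9% and 8.9% false positives, against at most 4.7% for any single reading.

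**5. How often would the branch be used?** The plan does not say which version of the Kolmogorov–Smirnov test applies. Under the same data models, with 20 to 40 pairs and the check made on the paired differences at the 5% level, the uncorrected test flags 0.5% to 5.2% of samples and the Lilliefors-corrected test 19% to 34%. If all 20 comparisons behaved this way, that is 20 × 0.005 = 0.1 to 20 × 0.052 = 1.0 tests, or 20 × 0.19 = 3.8 to 20 × 0.34 = 6.8 tests.

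**The case against.** The strongest reply is that this is a slip of the pen. The section pairs each t-test with a non-parametric partner, and the between-group partner is a rank test, so the Wilcoxon signed-rank test was probably meant. If the text is corrected before analysis, nothing is chosen after the fact. This is plausible, but it remains an inference, because no paired rank or sign test is named anywhere. A literal reader would dichotomise.

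The simulation is also open to criticism, and several points stand:

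- The McNemar readings are assumed, not taken from the plan. Dropping the 75th-percentile cut lowers the disagreement to about 53% (skewed) and 42% (heavy-tailed), and the 68-point loss comes from that cut alone.
- The best-of-four error rate supposes an analyst who tries every reading. Nothing in the documents suggests this.
- In both data models the differences T1 − T0 are symmetric, which suits the signed-rank test. Its performance with markedly asymmetric differences was not examined.
- The power figures cover all non-normal samples, not only those that fail the check. The plan also does not say whether the check applies to the differences or to each variable. For the skewed model at 30 pairs, the Lilliefors rate was about 29% on the differences and 50% on the variable.

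These points limit how much weight the figures can carry. They do not touch the defect, which is a mismatch between the named test and the type of data.

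**Conclusion.** The concern holds. The stated fallback is wrong for these variables, not merely short of detail, and it cannot be carried out without a decision that the plan does not make. This conclusion rests on the text alone.

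The consequences are limited. They fall on a conditional branch of a secondary, non-randomised within-arm comparison, with at most 20 tests (22 with the apoptotic index) and probably far fewer. The paired t branch, the primary between-group tests and the covariance analysis adjusted for baseline are unaffected. The power and error figures depend on assumed inputs and show only that the choice can matter. This should be corrected, but it does not threaten the trial's main result.

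**What to change.** In the Statistical Analysis section, replace McNemar's test with the Wilcoxon signed-rank test as the within-group fallback for non-normal continuous variables. McNemar need not be kept unless the team has a binary variable measured at both times, and none is described.

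It would help, in the same edit, to say that the normality check for this comparison applies to the T1 − T0 differences, to state which version of the Kolmogorov–Smirnov test is used and at what level, and to name the sign test if the differences are markedly asymmetric.

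The essential change is one term, made before the analysis. It needs no new data and no change of design, and Stata's signrank command performs the test.

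### McNemar, a test for paired binary data, is named for non-normal T1-T0 changes in continuous biomarkers; the Kolmogorov-Smirnov gate leading to it is under-specified

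*Combined protocol and SAP*

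**What the plan says.** All the relevant rules are in the Statistical Analysis section of the combined protocol and SAP. Biomarker data are log-transformed first.

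- **Between groups:** "Between groups comparisons at T0 and T1 will be made by means of t-Student test". The fallback is: "In case of non-normal distribution despite log-transformation of data we used a non-parametric alternative (U-Mann-Whitney test) instead".
- **Within groups:** "We will also compare within groups means differences between times T1 and T0", followed by "For this comparison we will use paired t-student test or McNemar test for normal or non-normal variable distributions respectively".
- **Normality check:** "Normality tests will be based on Kolmogorov- Smirnov". No correction, significance threshold or unit of testing (arm, pooled sample, residuals or differences) is stated.
- **Adjusted comparison:** "Covariance analysis will be used to compare the effect of high and low pressure on parameter analysed adjusting for baseline value of the biomarker". No normality switch is attached to it.

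The within-group comparison serves a stated secondary objective: "To analyse within groups (high and low pressure) differences between times T0 and T1 in the same remodelling and inflammatory physiological parameters". The two times are "Before starting surgery (T0) and 60 minutes after surgery started".

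**The concern.** A fallback must suit the data sent to it. Within groups, the quantity is the change in a logged mRNA level, which is continuous. McNemar needs each patient classed as yes or no at both times. For any marker judged non-normal the named analysis is therefore undefined. Someone would have to choose a cut-point, probably with the data in view, or change the test without a pre-stated reason.

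The gate decides how often this happens. Ordinary Kolmogorov-Smirnov (K-S) p-values assume that the normal mean and SD are known in advance. No reference values are given here, so both must come from the sample, and the ordinary test then becomes very conservative. Skewed or heavy-tailed logged data would mostly stay with the t-test, at some cost in power.

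The two faults interact. A gate that works properly sends more markers to a test that cannot be run, so mending the gate alone makes matters worse.

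**Working it through.** The plan gives no figure to reproduce: no sample size, alpha, effect size or residual shape is stated.

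**1. McNemar against the data (no assumptions needed).** With cut-point *c*, let *a* be the number of patients moving from ≤*c* at T0 to >*c* at T1, and *b* the number moving the other way. The statistic is (*a* − *b*)² / (*a* + *b*), or an exact binomial test of *a* out of *a* + *b*. Patients who stay on one side of *c* contribute nothing, however large their change. Without *c* neither *a* nor *b* exists.

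Comparisons exposed: 6 inflammatory + 4 remodelling markers = 10, and 10 × 2 arms = 20. Adding the apoptotic index gives 11 × 2 = 22. The secondary objective names only remodelling and inflammatory parameters, so 22 is an inference.

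The two binary secondary variables (need to change pressure; the surgeon's impression of pressure) are intraoperative items with no T0/T1 pair. No listed variable needs McNemar.

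**2. How often the gate fires (assumed 5% threshold, mean and SD from the sample).** D = max |F_n(x) − Φ((x − x̄)/s)|, where F_n is the empirical distribution function.

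| | n=20 | n=30 |
|---|---|---|
| Ordinary 5% critical D | 0.294 | 0.242 |
| Lilliefors 5% critical D | 0.192 | 0.159 |
| Normal samples flagged, ordinary K-S | 0.009% | 0.011% |
| t5 flagged, ordinary K-S | 0.4% | 0.7% |
| Gamma, skew 1, ordinary K-S | 0.2% | 0.5% |
| Lognormal sd 0.5, ordinary K-S | 1.5% | 3.7% |
| Lognormal sd 1, ordinary K-S | 20% | 43% |

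So it seldom fires for mild to moderate shapes and fires more often for gross ones. Better tests are not complete either. For t5 at n=20 to 30, Lilliefors detects 13-16% and Shapiro-Wilk 19-26%; for skew 1, 18-26% and 30-44%.

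**3. Paired power under the whole rule.** Assumed: McNemar exact at the pooled median, between-patient SD 1, gate on the differences. Shifts at n=20 are 0.8 (t3) and 0.7 (10% outliers with SD × 5).

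| Rule | t3, n=20 | Outliers, n=20 | t3, n=30 | Outliers, n=30 |
|---|---|---|---|---|
| As written (uncorrected K-S, McNemar) | 62.4% | 51.1% | 62.9% | 48.3% |
| Shapiro-Wilk, McNemar kept | 55.6% | 43.9% | 54.5% | 41.0% |
| Shapiro-Wilk, Wilcoxon | 70.0% | 66.8% | 73.8% | 69.4% |

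Both fixes gain 70.0 − 62.4 = 7.6 and 66.8 − 51.1 = 15.7 points at n=20. Mending the gate alone loses 62.4 − 55.6 = 6.8 and 51.1 − 43.9 = 7.2.

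**4. Replacing McNemar alone, n=20.** The swap matters only in samples that the gate flags, so the gain cannot exceed the firing rate.

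- Uncorrected K-S fires in 3% (t3) and 8% (outliers). A separate run of the same setting gives 63.2 → 64.4% (+1.2) and 52.3 → 55.5% (+3.2).
- Under a Lilliefors gate, power goes from about 59 to 70% (+11) and from about 49 to 64% (+15).

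Repeat simulations move these figures by a point or two.

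**5. Between groups at T1, uncorrected K-S rule v Lilliefors rule, n=20 per arm.** At T0 there is no pressure effect to detect.

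- Mild shapes (0.7 SD shift): t10 58.7 v 59.4%; t5 59.2 v 62.3%; gamma skew 0.7 58.9 v 60.1%; gamma skew 1 58.1 v 61.6%; lognormal sd 0.25 58.4 v 60.1%. The differences are 0.7 to 3.5 points.
- Stronger shapes: log-exponential 45.9 v 50.1%; t3 55.1 v 63.3%; 10% outliers 46.5 v 60.3%; lognormal sd 0.5 52.8 v 62.4%; lognormal sd 1 59.4 v 77.6%. The largest difference is 77.6 − 59.4 = 18.2 points.
- Normal data: 58.0% under either rule.
- Type I error: 4.5-5.6% under the K-S rule.

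**The case against.** The strongest reply is that little depends on this in practice. The covariance analysis has no switch and is the better between-group comparison. Type I error holds. The within-group tests serve a secondary objective. If K-S is uncorrected, McNemar is rarely reached, so naming it costs 1-3 points at n=20. Sample size, threshold, shapes and effects are all assumed. All of this stands, and it is why the gate is the secondary point here.

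It does not rescue McNemar. The section itself foresees markers that remain non-normal after logging, and for those the named test has no definition. The kindest reading, McNemar on up versus down (a sign test), still gives 65 v 72% for Wilcoxon (t3) and 57 v 67% (outliers) at n=20. If the sponsor replies that a corrected K-S was meant, the gate criticism weakens but the McNemar fault becomes larger.

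Three stronger readings are tempting and unsupported:

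- **A loss of 30-40 points within groups.** That compares always using McNemar with always using Wilcoxon. The plan uses McNemar only when the gate fires.
- **An uncorrected K-S test is planned.** The text names no correction but does not exclude one.
- **The between-group results are invalid.** Their error rate is near nominal. The cost is power, and it is small for mild departures.

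**Conclusion.** The point holds in two parts of unequal weight. Naming McNemar for continuous paired changes is wrong as written. That conclusion rests on the text alone and needs correcting whatever the sample size. The K-S gate is under-specified, and its weakness is conditional on ordinary p-values being used.

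At an assumed n=20, mending both faults raises paired power by about 7-8 points (t3) and 15-16 points (10% outliers). Both shapes are marked departures that would have to survive the log transformation. Between groups, the gate costs roughly 1-4 points against Lilliefors for mild shapes and up to about 18 only for the most marked shape tried. Neither part calls the baseline-adjusted covariance analysis into question.

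**What to change.** Make both wording changes in the same edit.

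1. Replace McNemar with the Wilcoxon signed-rank test on the T1-T0 differences and report the median change with it. Drop McNemar altogether, since no listed variable needs it.
2. Replace Kolmogorov-Smirnov with Shapiro-Wilk, or state the Lilliefors correction if that was intended. Give the threshold (for example 5%) and the unit: within arm or on residuals for between-group tests, and on the differences for paired tests.

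Do not make the second change without the first.

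The cost is two phrases and no new data. There are three limits to accept:

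- Signed-rank does not test the mean when differences are skewed. With lognormal sd 1 differences and zero mean change it rejects 25-34% of the time (paired t 11-13%), which is why the median change should be reported.
- A more sensitive gate uses rank tests more often. This loses nothing for normal data (58.0% under each rule), but 5-9 points for raw exponential outcomes with a proportional effect.
- Even Shapiro-Wilk misses many mild departures at this size. Choosing the tests in advance, or relying on the planned covariance analysis between groups, would avoid the gate.
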